## 7.5 Destruction and Return of Study Drug

If the study drug (those supplied by the sponsor or sourced by the investigator) are to be destroyed on site, it is the investigator's responsibility to ensure that arrangements have been made for the disposal, procedures for proper disposal have been established according to the applicable regulations, guidelines and institutional procedures, and appropriate records of the disposal have been documented. The unused study drugs can only be destroyed after being inspected and reconciled by the responsible BHV Study monitor or the sponsor's designee unless this is against institutional policy.

All unused and/or partially used study drug may be destroyed on site providing the site has an applicable standard operating procedure on file.

#### 8 ADVERSE EVENTS

An Adverse Event (AE) is defined as any new untoward medical occurrence or worsening of a pre-existing medical condition in a patient or clinical investigation patient administered an investigational (medicinal) product and that does not necessarily have a causal relationship with this treatment. An AE can therefore be any unfavorable and unintended sign (including an abnormal laboratory finding for example) symptom, or disease temporally associated with the use of the investigational product, whether or not considered relate to the investigational product.

Adverse events can be spontaneously reported or elicited during an open-ended questioning, examination, or evaluation of a patient. In order to prevent reporting bias, patients should not be questioned regarding the specific occurrence of one or more AEs.

There are two types of adverse events, Serious Adverse Events (SAE) and Non-Serious Adverse Events (AEs).

#### 8.1 SERIOUS ADVERSE EVENT

## 8.1.1 Definition of Serious Adverse Event (SAE)

An SAE is any event that meets any of the following criteria at any dose:

- Death
- Life-threatening
- Inpatient hospitalization or prolongation of existing hospitalization
- Persistent or significant disability/incapacity
- Congenital anomaly/birth defect in the offspring of a subject who received rimegepant
- Other: Important medical events that may not result in death, be life-threatening, or require hospitalization, may be considered an SAE when, based upon appropriate medical judgment, they may jeopardize the subject and may require medical or surgical intervention to prevent one of the outcomes listed in this definition. Examples of such events are (but not limited to):
  - o Intensive treatment in an emergency room or at home for allergic bronchospasm

- o Blood dyscrasias or convulsions that do not result in inpatient hospitalization
- o Development of drug dependency or drug abuse
- o Potential drug induced liver injury (see Section 8.1.5)
- Abuse or Overdose of medication
  - Potential study medication abuse (including cases of excessive non-compliance with study medication dosing instructions or patients who discontinue treatment without returning study medication) should be documented in the source record and reported as an AE or SAE as appropriate. Investigators must monitor patients for possible cases of abuse of study medication (patients taking study drug for non-therapeutic purposes, e.g. for psychoactive effects such as high or euphoria). Investigators should obtain more information and explanation from patients when there are study drug accountability discrepancies
  - Potential study medication overdose is defined in Section 8.1.3

#### **Definition of Terms**

Mild: Is usually transient and may require only minimal treatment or therapeutic intervention. The event does not generally interfere with usual activities of daily living.

Moderate: Is usually alleviated with additional specific therapeutic intervention. The event interferes with usual activities of daily living, causing discomfort but poses no significant or permanent risk of harm to the subject.

Severe: Interrupts usual activities of daily living, significantly affects clinical status, or may required intensive therapeutic intervention.

Life threatening: An AE is life threatening if the subject was at immediate risk of death from the event as it occurred; i.e., it does not include a reaction that if it had occurred in a more serious form might have caused death. For example, drug induced hepatitis that resolved without evidence of hepatic failure would not be considered life threatening even though drug induced hepatitis can be fatal.

Hospitalization: AEs requiring hospitalization should be considered SAEs. Hospitalization for elective surgery or routine clinical procedures that are not the result of AE (e.g., elective surgery for a pre-existing condition that has not worsened) need not be considered AEs or

SAEs. If anything untoward is reported during the procedure, that occurrence must be reported as an AE, either 'serious' or 'non-serious' according to the usual criteria.

In general, hospitalization signifies that the subject has been detained (usually involving at least an overnight stay) at the hospital or emergency ward for observation and/or treatment that would not have been appropriate in the physician's office or outpatient setting. When in doubt as to whether 'hospitalization' occurred or was necessary, the AE should be considered serious.

The following hospitalizations are not considered SAEs in BHV clinical studies (but may be considered non-serious AEs):

- 1. A visit to the emergency room or other hospital department <24 hours that does not result in an admission (unless considered "important medical event" or event that is life threatening);
- 2. Elective surgery, planned prior to signing consent;
- 3. Admissions as per protocol for a planned medical/surgical procedure;
- 4. Routine health assessment requiring admission (i.e., routine colonoscopy);
- 5. Admission encountered for another life circumstance that carries no bearing on health and requires no medical intervention (i.e., lack of housing, care-giver respite, family circumstances).

Disability/incapacitating: An AE is incapacitating or disabling if the experience results in a substantial and/or permanent disruption of the subject's ability to carry out normal life functions.

## 8.1.2 Collection and Reporting Serious Adverse Events

Following the patient's written consent to participate in the study, all SAEs, whether related or not related to study drug, must be collected, including those thought to be associated with protocol-specific procedures. All SAEs must be collected that occur during the screening period and up to and including the EOT visit. The investigator should report any SAE occurring after these time periods that is believed to be related to study drug or protocol-specific procedures.

An SAE report should be completed for any event where doubt exists regarding its status of seriousness.

If the investigator believes that an SAE is not related to the study drug, but is potentially related to the conditions of the study (such as a withdrawal of previous therapy or a complication related to study procedure), the relationship should be specified in the narrative section of the SAE Report Form.

SAEs, whether related or not related to study drug, must be reported to BHV (or designee) within 24 hours of the site's knowledge of the event. SAEs must be recorded in the EDC system on the AE and SAE electronic Case Report Form (eCRF). If the site cannot access the EDC to report the SAE within the required timeframe, the SAE should be reported using paper forms, which should be

The minimum information required for an initial SAE report is:

- Sender of report (Site number, Investigator name)
- Subject identification (subject number)
- Protocol number
- SAE term (if an SAE is being reported)

If only limited information is initially available, follow-up reports are required. If an ongoing SAE changes in its intensity or relationship to study drug or if new information becomes available, a follow-up SAE report should be sent within 24 hours to BHV (or designee) using the same procedure used for the transmission of the initial SAE.

All SAEs should be followed to resolution or stabilization.

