<sup>5 If the end of treatment vital signs from BHV3000-301/-302 were done on the same day of the screening visit for BHV3000-201, the vitals do not need to be completed at screening.

<sup>6 Height measured at the Screening Visit only. Weight, body temperature, respiratory rate, blood pressure, and heart rate will be collected at all time points where indicated. Sitting arterial systolic and diastolic blood pressure and radial artery pulse rate will be measured.

Procedure	Screening Visit	Observational Period (30 days, +/- 2 days)	Baseline Visit (Day 1)	Phone visit to confirm eligibility based on laboratory criteria 1	Week 2 (Day 15 +/- 2 days)	Week 4 (Day 29 +/- 2 days)	Weeks 8, 12, 16, 20, 24, 28, 32, 36, 40, 44, 48, 52 (or Early Termination) (all visits +/- 7 days)	Week 2 Follow-up Safety Visit (14 days after EOT visit +/- 2 days)
							only)	
Liver function tests (LFTs)	$X^7$		X		X	X	X	X
Lipid panel			X				X (Weeks 24 and 52/early termination only)	
ECG	X		X			X	X (Weeks 24 and 52/early termination only)	X
Urinalysis			X				X (Week 52/early termination only)	

 If the end of treatment laboratory tests from BHV-3000-301/-302 were done within 2 weeks of the screening visit for BHV-3000-201, the labs do not need to be completed at screening.

Procedure	Screening Visit	Observational Period (30 days, +/- 2 days)	Baseline Visit (Day 1)	Phone visit to confirm eligibility based on laboratory criteria	Week 2 (Day 15 +/- 2 days)	Week 4 (Day 29 +/- 2 days)	Weeks 8, 12, 16, 20, 24, 28, 32, 36, 40, 44, 48, 52 (or Early Termination) (all visits +/- 7 days)	Week 2 Follow-up Safety Visit (14 days after EOT visit +/- 2 days)
Urine Drug Screen for drugs of abuse 	X							
FSH, if applicable, to determine WOCBP status 	X							
Pregnancy Test	X (urine)		X (urine and serum)			X (urine)	X (urine)	X (urine)
AE and SAE assessment 10	X		X		X	X	X	X
Sheehan Suicidality Tracking Scale 	X		X		X	X	X	X
Clinical Drug Supplies/Study Supplies								

 If the end of treatment urine drug screen from BHV3000-301/-302 was done on the same day of the screening visit for BHV3000-201, the urine drug screen does not need to be completed at screening

<sup>9 If WOCBP status was determined in BHV-3000-301 or -302, the patient is considered to have the same status in BHV-3000-201.

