<sup>10 SAEs and AEs must be reported after patient signs informed consent.

<sup>11 If the end of treatment Sheehan Suicidality Tracking Scale from BHV3000-301/-302 was done on the same day of the screening visit for BHV3000-201, the Sheehan Suicidality Tracking Scale does not need to be completed at screening

Procedure	Screening Visit	Observational Period (30 days, +/- 2 days)	Baseline Visit (Day 1)	Phone visit to confirm eligibility based on laboratory criteria	Week 2 (Day 15 +/- 2 days)	Week 4 ( Day 29 +/- 2 days )	Weeks 8, 12, 16, 20, 24, 28, 32, 36, 40, 44, 48, 52 (or Early Termination) (all visits +/- 7 days)	Week 2 Follow-up Safety Visit (14 days after EOT visit +/- 2 days)
Dispense Study Medication 			X			X	X	
Administer study medication 				X	X	X	X	
Enter use of study medication in eDiary				X	X	X	X	
Return unused study medication to site for compliance check					x	X	X	
Electronic Diary Dispensed	X							
Electronic Diary returned/reviewed for completeness 14			X		X	Х	X	
Other Assessments								

-

<sup>12 Patients should finish a bottle of study medication before starting a new bottle. Study drug will be dispensed at monthly study visits as needed. Unscheduled visits to dispense study medication may be scheduled as needed.

<sup>13 Patients will be instructed that they can take their study medication at the onset of a migraine (mild, moderate or severe intensity), up to one tablet per calendar day. Patients must report each tablet they take in the eDiary.

<sup>14 Subjects with 6 or more missed evening diary reports per month, for 2 months (sequential or non-sequential months), should be discontinued for lack of study compliance.

Procedure	Screening Visit	Observational Period (30 days, +/- 2 days)	Baseline Visit (Day 1)	Phone visit to confirm eligibility based on laboratory criteria 1	Week 2 (Day 15 +/- 2 days)	Week 4 (Day 29 +/- 2 days)	Weeks 8, 12, 16, 20, 24, 28, 32, 36, 40, 44, 48, 52 (or Early Termination) (all visits +/- 7 days)	Week 2 Follow-up Safety Visit (14 days after EOT visit +/- 2 days)
Daily report of migraine occurrence and severity reported by patient in eDiary 		X	X		X	X	X	
Migraine Specified Quality of Life Questionnaire (MQoLQ) v 2.1			X				X (Weeks 12, 24, 36 and 52/early termination only)	

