# 4.3.4 Follow up Safety Visit

Patients will return to the study site 14 days after the Week 12/52/EOT Visit (+/- 2 days) to collect laboratory tests, vital signs, electrocardiography, and AEs. Investigators should assess patients for AEs consistent with drug dependency or withdrawal effects and report as appropriate (see Section 7.4).

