- TEAEs occurring in $\geq 2\%$ of subjects in any enrollment group after rounding. Percentages will be displayed rounded to integers, and AEs will be displayed in alphabetical order by SOC and PT.
- AEs occurring in $\geq 2\%$ of subjects in any enrollment group or subgroup level[^]
- AEs occurring in $\geq 5\%$ of subjects in any enrollment group by severity (primary safety endpoint, see Section 4.6.1)
- AEs occurring in $\geq 10\%$ of subjects in any enrollment group
- Exposure-adjusted AEs
- AEs related to study drug by severity*
- AEs related to study drug occurring in $\geq 2\%$ of subjects in any enrollment group or subgroup level[^]
- SAEs (primary safety endpoint, see Section 4.6.1)*
- Exposure-adjusted SAEs
- AEs leading to study drug discontinuation (primary safety endpoint, see Section 4.6.1)*
- Hepatic-related AEs by severity (secondary safety endpoint, see Section 4.6.2)[#]
- Hepatic-related SAEs[#]
- Hepatic-related AEs leading to study drug discontinuation (secondary safety endpoint, see Section 4.6.2)[#]
- Additional AEs of special interest: potential drug abuse[^]; CV; suicidality. Potential drug abuse AEs will be displayed in alphabetical order by severity and PT without SOC.

Endpoints marked with “*” will also be summarized by subgroup level and overall for all subgroups of interest specified in Section 4.2.6. Endpoints marked with “#” will also be summarized by subgroup level and overall only for extrinsic exposure factors (see Section 4.2.6). Endpoints marked with “^” will also be summarized by subgroup level and overall only for key extrinsic exposure factors (see Section 4.2.6).

Refer to the BHV3000 Core SAP for exposure-adjusted AEs. Calculations for on-treatment exposure-adjusted AEs will set reference start date to the study drug first dose date, reference end date to the study drug end dose date, and reference last date to the study drug last dose date + 7 days.

Follow-up AEs

Follow-up AEs will be summarized by SOC and PT for follow-up subjects by enrollment group and overall for the following endpoints:

- AEs by severity
- SAEs.

AEs in All Safety Analysis Periods Combined

AEs in all safety analysis periods combined (i.e., pre-treatment, on-treatment, and follow-up) will be summarized by SOC and PT for treated subjects by enrollment group and overall for the following endpoints:

- AEs leading to study drug discontinuation (primary safety endpoint, see Section 4.6.1)

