5.4 Analysis Periods

Analysis periods are defined as follows:

- Observational Period (OP): measurement date/time on or after the OP start date/time through the OP end date/time. This period is used to assess the number of migraine days per 4 weeks during the OP.
- Pre-treatment: measurement date/time on or before the study drug first dose date/time. This period is used to derive baseline values, and to assess safety and outcomes research endpoints.
- Post-enrollment: measurement date/time after the IWRS enrollment date/time through the EOT visit date + 7 days. This period is used to derive analysis visit windows for slotting observations.
- Follow-up: measurement date after the EOT visit date + 7 days. This period is used to slot observations.
- Long-term treatment (LTT): measurement date/time on or after the LTT start date/time through the LTT end date/time. This period is used to assess the number of migraine days per 4 weeks and number of tablets taken during LTT.
- On-treatment safety: measurement date/time after the study drug first dose date/time through the study drug last dose date + 7 days. Note that AEs with imputed start date equal to the study drug first dose date are part of this period (refer to the BHV3000 Core SAP for AE start date imputation). This period is used to assess safety endpoints on treatment.
- Follow-up safety: measurement date after the study drug last dose date + 7 days. This period is used to assess safety endpoints during follow-up.

See Section 5.3 for derived dates for determining analysis periods. If measurement time is missing or not collected, then the measurement date will be compared to the derived date.

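### Protocol Section 8.1.2 and the follow-up visit schedule disagree on whether unrelated SAEs are collected after EOT, which leaves the SAP's follow-up SAE table, and at most 7 days of its on-treatment table, with uncertain ascertainment

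*Protocol*

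**What the plan says.** **Protocol Section 8.1.2.** The end of full SAE collection is explicit: "All SAEs must be collected that occur during the screening period and up to and including the EOT visit". For later events the rule narrows: "The investigator should report any SAE occurring after these time periods that is believed to be related to study drug or protocol-specific procedures". The same section opens by asking for all SAEs after consent regardless of relationship, and it requires related and unrelated SAEs alike to be reported within 24 hours of the site learning of them.

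**Protocol Section 4.3, Tables 1 and 2.** Both schedules have a row for "AE and SAE assessment" that is marked at the follow-up safety visit. The row's footnote, the same in both tables, reads "SAEs and AEs must be reported after patient signs informed consent". It gives a start, but no end and no relatedness limit.

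**Protocol Section 4.3.4.** Patients return 14 days (plus or minus 2) after EOT to "collect laboratory tests, vital signs, electrocardiography, and AEs", again without restriction.

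**SAP Section 5.4.** On-treatment safety runs from first dose "through the study drug last dose date + 7 days". Follow-up safety is everything after that, with no stated end.

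**SAP Section 4.8.2.** SAEs are tabulated on treatment (labelled a primary safety endpoint) and again in follow-up: "Follow-up AEs will be summarized by SOC and PT for follow-up subjects by enrollment group and overall", with SAEs as one of the listed endpoints. The follow-up AE overview has separate rows for all SAEs and for related SAEs.

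**The concern.** Read alone, 8.1.2 places a causality filter on SAEs from the day after EOT. The SAP tables draw no line at EOT. The all-SAE row of the follow-up overview, beside a related-SAE row, only makes sense if unrelated events are expected in the data. The follow-up denominator (SAP Section 3) is every treated subject whose last contact falls in that period, with no matching filter. The on-treatment exposure-adjusted SAE table also uses last dose plus 7 days as its last reference date.

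The study is open label and single arm, with no data monitoring committee and no comparator that shares the same gap. If some sites work from 8.1.2 and others from the schedule, they will report different events, and nothing in the SAP would show which rule a given count reflects. Section 4.3.4 also asks investigators to look for dependency and withdrawal effects at the follow-up visit, so the collection rule should be clear there.

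**Working it through.** The plan gives no figure to reproduce on this point. The check compares the windows in days.

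**Inputs**
- End of all-SAE collection under 8.1.2: the EOT visit, inclusive.
- Follow-up visit: EOT + 14 days (plus or minus 2), from Sections 4.1 and 4.3.4.
- On-treatment window: to last dose + 7 days (SAP 5.4).
- The SAP's EOT date is the later of the last treatment-phase diary date and the last visit other than follow-up (SAP 5.3), so it cannot precede the last dose.
- Treatment length: 364 days (2-8 and 9-14 groups) or 84 days (every-other-day group).

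**Formulas.** Let g = EOT date minus last dose date, with g ≥ 0.
- On-treatment days after EOT = max(0, 7 − g)
- Follow-up safety days up to the 14-day visit = 14 + g − 7 = 7 + g
- Of these, days after EOT = min(14, 7 + g)

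| g (days) | On-treatment days after EOT | Follow-up days to the visit | Of which after EOT |
|---|---|---|---|
| 0 | 7 | 7 | 7 |
| 3 | 4 | 10 | 10 |
| 7 | 0 | 14 | 14 |
| 14 | 0 | 21 | 14 |
| 28 | 0 | 35 | 14 |

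For g ≤ 7 the whole follow-up safety period lies after EOT. For g > 7 its first g − 7 days precede EOT and are fully collected under either rule.

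**On-treatment table, largest possible share (g = 0, first dose on day 1)**
- 52-week completer: 7/(364 + 7) = 7/371 = 1.9%
- 12-week completer: 7/(84 + 7) = 7/91 = 7.7%; with g = 1, 6/90 = 6.7%
- Early terminator, for example last dose and EOT on day 28: 7/(28 + 7) = 20%
- Pooled, with 1800 subjects on 52 weeks and 200 on 12 weeks, all completing and all dosing on the EOT day: (2000 × 7)/(1800 × 371 + 200 × 91) = 14,000/686,000 = 2.0%

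**As-needed dosing.** The documents give no data on the gap between last dose and EOT. Assume one dose per attack and a daily dosing probability of attacks per month divided by 30, so that g is geometric. The range is 2 to 14 attacks per month.

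| Attacks per month | P(g < 7) | Mean on-treatment days after EOT | Share of 371 days | Share of follow-up time after EOT (14-day visit) |
|---|---|---|---|---|
| 2 | 0.38 | 1.6 | 0.4% | 59% |
| 8 | 0.89 | 4.6 | 1.2% | 97% |
| 14 | 0.99 | 5.9 | 1.6% | over 99% |

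The last column is mean post-EOT follow-up days over mean follow-up days. Moving the visit to day 12 or day 16 changes the 2-per-month figure to 55% or 62% and hardly moves the others. More frequent dosing pushes results toward the ceilings above.

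**If Tables 1 and 2 and Section 4.3.4 govern instead**, the days with related-only reporting up to the follow-up visit are 0 in both tables.

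**The case against.** A reader might infer that both SAE tables undercount by design and that the primary endpoint is biased downward. The documents do not support that.

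- Both schedules, their footnotes and Section 4.3.4 call for collection at the follow-up visit without a relatedness filter. Other sentences of 8.1.2 ask for SAEs regardless of relationship, and Section 8.2.1 has non-serious AEs followed and reported as SAEs if they become serious. An undercount depends on which text a site follows. This objection stands: what is shown is a contradiction, not a planned omission.
- The protocol's primary endpoint refers to the treatment period, and 8.1.2 collects everything through EOT. Only the on-treatment SAE table is labelled primary in the SAP. This stands: the primary table is touched for 7 days at most, and the larger percentage for completers belongs to a group of about 200 out of 2000.
- The SAP nowhere claims complete collection. It analyses observed data only (Section 4.2.8) and plans no comparison of SAE frequency between periods. This also stands, but a reader of an all-SAE row would still take it to mean all SAEs.
- The SAP rests on protocol Version 6, which added a cohort on CGRP biologics. The protocol supplied has no such cohort and so appears to be an earlier version. AE counting rules sit in a Core SAP that was not supplied. The mismatch between protocol and SAP may therefore already be resolved.

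None of this removes the conflict within the supplied protocol over unrelated SAEs between EOT and the follow-up visit.

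**Conclusion.** The point holds as an internal contradiction in the protocol with a bounded effect on two SAP tables. It should be fixed, but it does not undermine the primary endpoint.

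The follow-up SAE table carries most of the exposure: all of its period when the last dose is within 7 days of EOT, and only the post-EOT part otherwise. The on-treatment table is exposed for no more than 7 days per subject, about 2.0% of pooled time at the ceiling, and not at all when the last dose was 7 or more days before EOT.

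These sizes describe time at risk of incomplete reporting if 8.1.2 alone is followed. They are not counts of missed events. Only SAEs judged unrelated could be lost, because related ones remain reportable throughout, and the documents give no SAE rate from which to estimate a number. The ceilings rest on the scheduled treatment lengths with dosing up to the EOT day. The as-needed figures rest on the assumed dosing pattern.

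**What to change.** Reconcile Section 8.1.2 with Tables 1 and 2 and Section 4.3.4. State that all SAEs, whether or not related, are collected from consent through the Follow-up Safety Visit, and that after that visit only SAEs believed related to study drug or procedures are reported. Because the on-treatment window ends no later than 7 days after EOT, it then falls wholly inside full collection for subjects who attend the follow-up visit. Check the change against the Version 6 wording before making it.

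The SAP's follow-up safety period has no end date, so it should also say which rule applies to events after the follow-up visit.

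If 8.1.2 is kept as it is, footnote the on-treatment and follow-up SAE tables to say that ascertainment after EOT is limited to SAEs believed related.

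The cost is one protocol sentence, one SAP note and a few more SAE reports. The visit and its SAE assessment are already scheduled.
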